Dependent measures are vowel recognition, word recognition in quiet, and sentence recognition in noise. Linear Mixed Models (LMM) will be used to assess the main effects of group (default vs place-based) and interval (activation, 1, 3, 6, & 12 mos), and the interaction between group and interval on each measure, with a significance criterion of $\alpha=0.05$. Aided acoustic audibility as measured with the Speech Intelligibility Index (SII) will be included as a within-subjects variable to control for differences in residual hearing. Subject demographic data to be reported include: gender, age, unaided thresholds, AID of the most apical electrode, and mismatch. Mismatch will be quantified as the absolute semitone deviation at 1500 Hz (~267° using the SG function), which has been shown to be an important region for frequency alignment in vocoder simulations. Reduced models will assess the main effects of map (default vs place-based) and interval (activation & 12 mos), and the two-way interaction for the within-subjects comparison. Results from the NH control group will be compared to EAS users at activation, to corroborate effects of mapping approach in the findings from the CI subjects.

For Aim 2, we plan to investigate the binaural hearing abilities of EAS users listening with a place-based map versus a default map. We plan to recruit 24 subjects from the experiments under Aim 1 with thresholds ≤ 65 dB HL at 125 Hz in the contralateral ear. For NH subjects listening to a bilateral CI simulation, SRM is ~8 dB (95% CI: ~7 dB) with no interaural mismatch and ~4 dB (95% CI: ~11 dB) with an interaural mismatch of 1 mm (Xu et al., 2020). Similar results are obtained with bilateral CI recipients (Hu et al., 2018). Based on these data, our experiment is powered to observe effect sizes of $d \geq 0.90$ ($\alpha < 0.05$, $1 - \beta = 0.8$).

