Binaural hearing will be assessed in the soundbooth, using an 11-speaker arc spanning -90° to 90°. Subject listen with EAS+HA or EAS+NH at the 1, 3, 6, & 12-month intervals. Binaural hearing measures include: 1) spatially masked sentence recognition, 2) localization, and 3) subjective benefit. Spatially masked sentence recognition will be completed, with performance calculated as SRM_{EAS} and SRM_{Contra}. The dB SNR for each subject will be determined at the 1-month interval in the co-located condition, by decreasing the dB SNR from 10 dB to 0 dB in 5 dB steps until the subject scores <50% correct. Subjects will be evaluated at the same SNR for the subsequent intervals. Localization will be assessed by calculating the root-mean-squared (RMS) error of sound source identification using 200-ms noise bursts at varied intensity levels (52, 62, or 72 dB SPL). Subjective benefit will be assessed using the Speech, Spatial, and Qualities of Hearing Scale (SSQ;

Gatehouse & Noble, 2004), with results evaluated on the 3 subscales and 10 pragmatic subscales (defined by Gatehouse & Akeroyd, 2006).

The primary analysis is the effect of group (default vs place-based) on SRM_{EAS} , SRM_{Contra} , and localization. An LMM will assess the main effects (group and interval) and the associated interaction, with a significance criterion of $\alpha < 0.05$. Secondary analyses will include the effect of group on subjective benefit, assessed for the Spatial Hearing subscale, and relevant pragmatic subscales, including: 1) Speech in Speech Contexts, 2) Segregation of Sounds and Objects, and 3) Listening Effort.

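### If the 1-month run that sets each subject's SNR also supplies the 1-month co-located score, 1-month SRM is biased upward for subjects stopped at 10 or 5 dB, and the interval effect leans toward a fall

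*Combined protocol and SAP*

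**What the plan says.** The relevant text is the Aim 2 part of the combined protocol and SAP, under Statistical Power and Design.

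- Setting the SNR: "The dB SNR for each subject will be determined at the 1-month interval in the co-located condition", and this is done "by decreasing the dB SNR from 10 dB to 0 dB in 5 dB steps until the subject scores <50% correct".
- Use of that SNR: "Subjects will be evaluated at the same SNR for the subsequent intervals".
- Outcome visits: "Subject listen with EAS+HA or EAS+NH at the 1, 3, 6, & 12-month intervals". The visit that sets the SNR is therefore also the first outcome visit.
- Analysis: "An LMM will assess the main effects (group and interval) and the associated interaction". The stated primary contrast is between groups: "The primary analysis is the effect of group (default vs place-based) on SRM_{EAS" (the sentence goes on to the other two outcomes).
- Size: "We plan to recruit 24 subjects from the experiments under Aim 1".

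The text does not say which 1-month co-located score enters the analysis. It gives no formula for SRM, no list length, and no rule for a subject who still scores 50% or more at 0 dB.

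**The concern.** A run at 10 or 5 dB ends the search only if its observed score is below 50%. A subject whose true score there is a little above 50% is stopped only when the list happens to err downward. A subject whose true score is a little below 50% is stopped unless it errs upward. Among stopped runs the list error is therefore negative on average.

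SRM is, by its meaning, the gain in a spatially separated condition over the co-located one. If the stopping score is the 1-month reference, its downward error raises SRM_EAS and SRM_Contra together. At 3, 6 and 12 months the co-located score comes from a new list at a fixed SNR, has no such selection, and regresses upward.

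What is at stake is the interval main effect, a named term in the model for two of the primary outcomes. SRM could appear to decline after 1 month, or a real gain with listening experience could be partly hidden, for a reason that has nothing to do with hearing. Recruiting more subjects would not remove this.

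**Working it through.** **No figure to reproduce.** The plan gives no number for this quantity. The check takes the stopping rule from the text and everything else by assumption.

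**From the documents:** levels of 10, 5 and 0 dB; stop when the co-located score is below 50%; 0 dB is the lowest level; 24 subjects; visits at 1, 3, 6 and 12 months.

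**Assumed, not in the documents:** SRM is scored in percentage points as separated minus co-located; percent correct is logistic in SNR with slope 0.2 to 0.4 per dB (at the midpoint 100 × slope / 4, that is 5 to 10 points per dB); the SNR giving 50% correct has mean 3 to 8 dB and SD 5 dB across subjects; list-score error has SD 5 to 10 points; there is no true change over time.

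**Step 1, direction.** Let a subject's true score at a level be m and the list-error SD be s. Given a stop at 10 or 5 dB,

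mean error = −s × φ(a) / Φ(−a), with a = (m − 50) / s.

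This is negative for every m. Examples:
- m = 50, s = 5: −5 × 0.399 / 0.5 = −4.0 points.
- m = 50, s = 10: −10 × 0.399 / 0.5 = −8.0 points.
- m = 55, s = 5: a = 1, so −5 × 0.242 / 0.159 = −7.6 points, but such a subject is stopped only 16% of the time.

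For subjects whose true score is far below 50% the selection hardly acts, so the average over subjects is much smaller than these cases.

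**Step 2, the 0 dB level.** The 0 dB run is kept whatever its score. Whether a subject gets there depends on the errors of the earlier lists, not on the 0 dB list. Its mean error is zero.

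**Step 3, average over subjects.** The rule was simulated with 400,000 subjects per setting, at mean 50% points of 3, 5 and 8 dB. The table shows how far the stopping score falls below the true score, in points.

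| Setting (error SD; slope; mean 50% point) | Share stopped at 10 or 5 dB | Bias in those stopped | Bias over all |
|---|---|---|---|
| 5; 0.4; 3 dB | 35% | 0.76 | 0.26 |
| 5; 0.4; 8 dB | 72% | 0.49 | 0.36 |
| 10; 0.2; 3 dB | 36% | 5.77 | 2.08 |
| 10; 0.2; 8 dB | 71% | 3.72 | 2.65 |

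The columns agree: 0.71 × 3.72 = 2.64, and 0.36 × 5.77 = 2.08. Over the grid, 28% to 65% of subjects reach 0 dB, with no bias beyond simulation error. Bounding scores to 0–100% moves the smallest value among those stopped from 0.49 to 0.44. The ranges are thus about 0.3 to 2.7 points overall and about 0.4 to 6 points among those stopped at 10 or 5 dB. Both SRM measures at 1 month are too high by the same amounts.

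A second grid (slope 4 to 8 points per dB, error SD 4 to 10, mean 50% point 2 to 8 dB, SD 4 dB) gave 0.2 to 3.6 points overall. With slope 6 and error SD 6, the bias fell to 0.02 to 0.3 points when half or more of the subjects scored 50% or above even at 0 dB. A fresh list at the chosen SNR gave zero bias within simulation error.

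**Step 4, against the noise.** Counting list error only, SRM at one visit has variance 2s². For 1 month against the mean of three later visits in 24 subjects, SE = √[2s²(1 + 1/3) / 24] = s/3, which is 1.67 points at s = 5 and 3.33 at s = 10. The bias is 0.26 / 1.67 = 0.16 to 2.65 / 3.33 = 0.80 of one standard error.

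**Step 5, the group contrast.** The same rule applies in both groups. If the groups' 50% points differed by 3 dB (assumed), the 1-month bias would differ between them by 0.27 to 0.61 points. Averaged over four visits this is 0.27 / 4 = 0.07 to 0.61 / 4 = 0.15 points.

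**The case against.** **Reuse is not written down.** The plan says how the SNR is determined. It does not say that the determining run is scored as an outcome. In a short design text without list counts or an SRM formula, silence about one more list is weak evidence that none is run. This stands: the point must be conditional. Against it, the only visits for which testing at the chosen SNR is specified are the later ones, so someone following the text literally would have just the stopping run at 1 month.

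**Not every run is selected.** A reader might infer that all 1-month scores were kept for being low. The documents do not support that, because the search has a floor at 0 dB and the run there is kept regardless.

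**The primary question is barely touched.** A reader might infer that the comparison of default and place-based maps is compromised. It is not. The primary contrast is by group, the rule is common to both groups, and Step 5 puts the distortion at a small fraction of a point. Localization and the subjective scale do not use this score at all.

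**The bias is small and its size is assumed.** It is below one standard error of the interval contrast throughout the first grid, and real within-subject variation would lower that ratio further. The range is about nine-fold because nothing in the documents anchors the inputs. This also stands. It limits the importance of the point but does not remove it: given reuse, the direction follows from the rule whatever the inputs, and the list length that would rule out the larger values is not stated.

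**Conclusion.** The point holds in conditional form. If the stopping run serves as the 1-month co-located score, 1-month SRM_EAS and SRM_Contra are biased upward for subjects stopped at 10 or 5 dB, and the interval effect is biased toward a fall after 1 month. The size, about 0.3 to 2.7 points overall and 0.4 to 6 points among those stopped at 10 or 5 dB, rests wholly on the assumed slope, list error and spread of 50% points, and on SRM being a difference in percent correct from the co-located condition. It would be near zero if most subjects reach 0 dB. The group-by-interval term is affected only to the extent that the groups differ in how often they stop at 10 or 5 dB. This is a modest, inexpensive improvement to a secondary reading of the model, not a threat to the primary contrast.

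**What to change.** State that the descending runs serve only to choose the SNR. Then score the 1-month co-located condition from a fresh list at that SNR, in the same session as the spatially separated conditions and in random order with them, and use only that score for 1-month SRM. Write out the SRM formula, and state what happens when a subject still scores 50% or more at 0 dB.

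The cost is one extra sentence list per subject at 1 month: a few minutes for each of 24 subjects, with no new visit, staff or equipment.

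If 1-month testing is already complete, record which score was used. If the stopping run was reused, add a sensitivity analysis of SRM that omits the 1-month interval. This needs no new data but gives up the earliest time point in that analysis.

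### Aim 2 localization model: pre-specifying the contralateral listening condition (EAS+HA or EAS+NH) as a covariate is a cheap improvement, not the correction of an error

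*Combined protocol and SAP*

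**What the plan says.** All references are to the combined protocol and SAP, under Statistical Power and Design.

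- **Who is tested.** Aim 2 takes 24 of the Aim 1 subjects, those "with thresholds ≤ 65 dB HL at 125 Hz in the contralateral ear".
- **How they listen.** "Subject listen with EAS+HA or EAS+NH at the 1, 3, 6, & 12-month intervals". The second ear is therefore not in the same condition for everyone.
- **Primary analysis.** "The primary analysis is the effect of group (default vs place-based") on SRM_EAS, SRM_Contra and localization. The model is given as "An LMM will assess the main effects (group and interval) and the associated interaction". No covariate is named.
- **Outcomes.** "Localization will be assessed by calculating the root-mean-squared (RMS) error of sound source identification". For the SRM tests, "The dB SNR for each subject will be determined at the 1-month interval in the co-located condition", and "Subjects will be evaluated at the same SNR for the subsequent intervals".
- **Power.** For Aim 2, "our experiment is powered to observe effect sizes of" d ≥ 0.90, with 80% power and alpha 0.05. The inputs are SRM values in dB.
- **Randomisation.** The Aim 1 text describes allocation to two groups and mentions neither a ratio nor stratification by the opposite ear.
- **SII.** The audibility covariate appears in the Aim 1 analysis paragraph and is not repeated for Aim 2.

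**The concern.** Aim 2 measures binaural hearing, so the contralateral ear supplies one of the two inputs to each primary outcome. If EAS+HA and EAS+NH subjects differ in outcome, two things follow under the planned model. The difference stays in the error term of a 24-subject comparison. And if the two conditions fall unevenly between the arms, that sample's estimate is shifted and the model has no term to correct it.

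The rationale is strongest for localization, because RMS error is an absolute score with no individual reference. It is weaker for SRM_EAS and SRM_Contra: SRM is a within-subject difference, measured at an SNR set from each subject's own co-located score, so some of the effect of the second ear may already cancel.

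**Working it through.** **Inputs from the plan:** 24 subjects, two groups, four visits, d = 0.90, 80% power, alpha 0.05.

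**Assumptions, none stated in the plan:** 12 vs 12, two-sided test, complete data, compound symmetry with within-subject correlation ρ, and d in single-visit SD units. The share q of between-subject variance explained by HA/NH, and the HA/NH mix, are both unknown.

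**1. The plan's own figure.** With one observation per subject, a 12 vs 12 t test (22 df) has 56% power at d = 0.90 and a detectable d of 1.20. The stated 0.90 is recovered if the group effect is tested on the mean of four visits with ρ = 0.42:

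variance = ρ + (1 − ρ)/4 = 0.42 + 0.145 = 0.565; noncentral t, 22 df: power 80.0%, detectable d 0.90.

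The value 0.42 is chosen to match the plan, not taken from it. At ρ = 0.7 the variance is 0.775 and the power 66.8%.

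**2. Adding one covariate.** Residual variance becomes ρ(1 − q) + (1 − ρ)/4. The squared standard error is (1/12 + 1/12) × residual variance × (1 + 1/20), where the last factor is the average cost of chance imbalance in one covariate. The df fall to 21. Power at d = 0.90:

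| q | Residual variance (ρ = 0.42) | Power, ρ = 0.42 | Power, ρ = 0.7 |
|---|---|---|---|
| planned model | 0.565 | 80.0% | 66.8% |
| 0 | 0.565 | 77.9% | 64.5% |
| 0.1 | 0.523 | 81.0% | 68.6% |
| 0.2 | 0.481 | 84.1% | 73.1% |
| 0.3 | 0.439 | 87.2% | 77.9% |

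Break-even is q = 0.070 (ρ = 0.42) or 0.057 (ρ = 0.7). A simulation with a binary covariate, 12 of 24 EAS+NH and random 12:12 splits (10,000 runs, ρ = 0.42, q = 0.3) gave 79.7% unadjusted and 87.3% adjusted. Simulated type I error was 4.7% to 5.4%.

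**3. Dependence on the mix.** With a share p in EAS+NH and an HA-NH gap g (single-visit SD), q = g² × p(1 − p)/ρ. For a fixed gap, q is therefore largest at p = 0.5. At ρ = 0.42, q = 0.2 with 12 of 24 means g = √(0.2 × 0.42/0.25) = 0.58, and q = 0.3 means g = √(0.3 × 0.42/0.25) = 0.71. Keeping the gap and the total variance fixed (planned model 80.0%):

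| EAS+NH of 24 | p(1 − p) | q, gap 0.58 | Power | q, gap 0.71 | Power |
|---|---|---|---|---|---|
| 12 | 0.250 | 0.200 | 84.1% | 0.300 | 87.2% |
| 6 | 0.188 | 0.150 | 82.5% | 0.225 | 84.9% |
| 4 | 0.139 | 0.111 | 81.3% | 0.167 | 83.0% |
| 2 | 0.076 | 0.061 | 79.8% | 0.092 | 80.7% |

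**4. Chance imbalance.** From the hypergeometric distribution, the arms differ by 4 or more in their EAS+NH count with probability 9%, 15%, 19% or 22% if 4, 6, 8 or 12 of 24 are EAS+NH. With 3 or fewer this cannot happen. An 8 vs 4 split (12 of 24 EAS+NH) shifts the unadjusted difference by 4/12 of the gap: 0.58/3 = 0.19 SD, or 0.71/3 = 0.24 SD.

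**The case against.** The strongest reply is that nothing is broken. Group is randomised, the unadjusted test holds its 5% level over all allocations, and adding a precision covariate to a valid analysis is a matter of choice. That stands. A reader might infer from the missing term that the group comparison is biased or confounded by the second ear. The documents do not support that: an uneven split shifts the estimate in a particular sample, not on average. The 8 vs 4 example is also a selected case, and it needs a mix that the plan does not give.

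The second reply is that the benefit is not shown. The documents give no HA/NH mix, no HA/NH effect on any outcome, no localization variance and no between-visit correlation. This also stands. Below about 7% of variance explained the covariate costs power, and nothing in the plan shows which side of that line applies. The d = 0.90 benchmark comes from SRM data, so no figure above is specific to localization; the case for localization is reasoned from how the outcome is scored.

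A reader might also infer that the mix hardly matters, because power is almost the same for any mix if q is held constant. But constant q requires the HA-NH gap to grow as one condition becomes rarer. For a given gap the gain shrinks, as step 3 shows.

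Lastly, the SII term in Aim 1 might be read as a precedent for adjusting for the opposite ear. Nothing in the text says that it covers that ear. It shows only that the stated adjustment does not reach the Aim 2 models.

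What survives is narrow. The condition has to be known in order to run the tests, the worst-case cost is small, and adjustment is credible only if fixed before the results are seen.

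**Conclusion.** The omission is real and the point holds as a cheap, optional-in-principle improvement that is worth making for localization. It is not a validity problem. Under the stated assumptions the covariate moves power at d = 0.90 from 80% to between 78% (no prognostic value) and 87% (30% of between-subject variance explained, even mix). With 2 of 24 in the smaller condition, the same gaps give essentially no gain. At ρ = 0.7 the corresponding range is 67% unadjusted to between 64% and 78%. Confidence is medium: the model text is clear, but the size of the benefit rests on an HA/NH effect and mix that the documents do not give.

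**What to change.** Before analysis, add to the Aim 2 plan:

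- The localization LMM includes the contralateral listening condition (EAS+HA vs EAS+NH), fixed at Aim 2 entry and not updated, as one main-effect covariate beside group, interval and their interaction.
- One firm rule, decided from the counts alone: if 3 or fewer subjects are in the smaller condition, the model is fitted as now planned, without the covariate.
- Using the same term for SRM_EAS and SRM_Contra is optional, with a smaller gain expected. Whichever choice is made should be stated in advance.

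Cost: a line or two of analysis text, one degree of freedom, and about 2 points of power (80% to 78%) if the condition predicts nothing. No further subjects or measurements are needed.

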Place-Based Mapping in EAS Listeners

NCT04722042

Modified Date: 2/17/2025

Statistical Power and Design

For the first experiment under Aim 1, we plan to investigate monaural speech for EAS users listening with a place-based versus a default map. We plan to recruit 40 subjects from the UNC Adult CI Program (~140 surgeries/year) at initial activation (~2-4 weeks postop). Inclusion criteria are 18-65 years of age, MED-EL array recipient, and a postoperative unaided detection threshold of ≤ 65 dB HL at 125 Hz. Recruitment is limited to recipients of one manufacturer to control for number and separation of electrodes, as well as coding strategy. Subjects will be fit with the Sonnet2EAS device. Subjects must identify English as their native language since test materials are in English. Subjects will be excluded if they report or present with a cognitive delay or impairment, as indicated with the Mini Mental State Examination (Folstein, Folstein, & McHugh; 1975). Subjects will be randomized into one of 2 groups: 1) default map, or 2) place-based map. In addition to these 40 CI users, age-matched NH listeners will be recruited for reference.

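### The Aim 2 primary model omits implanted-ear hearing at entry, an already measured baseline covariate that could sharpen a 24-subject comparison

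*Combined protocol and SAP*

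**What the plan says.** All of this is in Statistical Power and Design.

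- **Eligibility (Aim 1).** Subjects enter at initial activation and must have "a postoperative unaided detection threshold of ≤ 65 dB HL at 125 Hz". The sentence does not name the ear. That the threshold is postoperative, and that Aim 2 adds a separate contralateral criterion, indicates the implanted ear.
- **Allocation.** "Subjects will be randomized into one of 2 groups: 1) default map, or 2) place-based map". The ratio is not stated.
- **Aim 1 model.** Aided acoustic audibility, measured by the Speech Intelligibility Index (SII), "will be included as a within-subjects variable to control for differences in residual hearing". Unaided thresholds are also to be reported, as descriptive data.
- **Aim 2 sample.** "We plan to recruit 24 subjects from the experiments under Aim 1", restricted to those "with thresholds ≤ 65 dB HL at 125 Hz in the contralateral ear". Nothing further is asked of the implanted ear.
- **Aim 2 primary analysis.** The outcomes are SRM_EAS, SRM_Contra and localization, tested at 1, 3, 6 and 12 months. "An LMM will assess the main effects (group and interval) and the associated interaction, with a significance criterion of" α < 0.05. No SII, threshold or other hearing term is listed.

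**The concern.** The plan treats residual hearing as a source of outcome variation in Aim 1 and is silent on it in Aim 2, although the subjects are the same people. Implanted-ear acoustic hearing plausibly affects access to low-frequency binaural cues, so differences in it at entry may add to the spread of the Aim 2 outcomes.

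Group is a between-subject factor. The plan does not state the random-effects structure. A random subject intercept would account for repeated visits, but it would not take between-subject differences in hearing out of the standard error of the group effect. A baseline covariate can.

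What is at stake is the width of the confidence interval for the map effect in a small comparison, and how far one chance imbalance in hearing can move the estimate.

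**Working it through.** **The plan's own figure.** Aim 2 is said to be powered for d ≥ 0.90 at 80% power. With 12 per group (1:1 assumed) and a two-sided 5% t-test on one value per subject, d = 0.90 gives 56% power, and the detectable d at 80% power is 1.20. About 80% is reached with a paired t-test on 12 subjects (81%), or by averaging the four visits with a between-visit correlation of about 0.42. The documents state neither. That is a separate matter and this point does not rest on it. It shows only that there may be little precision to spare.

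**Inputs for the precision check.**
- n = 24 (Aim 2 sample).
- One summary value per subject, such as the mean over visits. This is a simplification of the mixed model.
- r, the within-group correlation between the entry threshold and that summary. The documents do not give it; 0.3, 0.5 and 0.6 are assumed.

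**Formula.** Residual degrees of freedom are 24 − 2 = 22 without the covariate and 24 − 3 = 21 with it. With the covariate balanced between groups,

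SE ratio = √[(1 − r²) × 22/21], and equivalent n = 24 / ratio².

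**Results.**
- r = 0.3: √(0.91 × 1.0476) = 0.976. SE about 2% lower; equivalent n = 25.2.
- r = 0.5: √(0.75 × 1.0476) = 0.886. SE about 11% lower; equivalent n = 30.5.
- r = 0.6: √(0.64 × 1.0476) = 0.819. SE about 18% lower; equivalent n = 35.8.

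**Break-even and worst case.** The ratio equals 1 when r² = 1/22, that is r = 0.21. At r = 0 it is √(22/21) = 1.024, so a useless covariate costs about 2% in SE.

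**Chance imbalance.** With 12 per group, the standard error of the difference in mean threshold is √(2/12) = 0.41 SD. An imbalance of that size moves the unadjusted group difference by r × 0.41 outcome SDs: 0.12, 0.20 or 0.24 at r = 0.3, 0.5 or 0.6. The unadjusted standard error already allows for this, so it is not bias. Adjustment removes it from the estimate.

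**The case against.** **The model is valid as written.** Randomisation protects the group comparison, and leaving Aim 1's SII term out of Aim 2 can be defended. SII is an aided measure described as varying within subjects, and a hearing value taken after randomisation might be affected by the assigned map. This stands. The contrast with Aim 1 shows that the sponsor regards residual hearing as relevant; it does not show that Aim 2 should copy the Aim 1 term. It is a reason to use only a baseline value.

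**The gain is speculative.** No document links the unaided 125 Hz threshold to spatial release from masking or localization. Entry is capped at 65 dB HL, which narrows the covariate's range and tends to weaken its correlation with outcome. This also stands, and it limits the claim to a modest one.

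**A stronger reading is tempting.** A reader might infer that subjects who later lose acoustic hearing cease to be eligible, remain in the comparison wrongly, and dilute the map effect. The documents do not support this:
- The 65 dB HL limit is an entry criterion, not a retention rule. Keeping randomised subjects in their assigned group is normal practice.
- No rate of hearing loss is given.
- Nothing says the map effect disappears after loss. The Aim 2 power argument rests on a bilateral CI simulation in which spatial release falls from about 8 dB to about 4 dB with a 1 mm interaural mismatch, and it says bilateral CI recipients give similar results. Frequency alignment could therefore still matter without acoustic hearing.
- A threshold above 65 dB HL at 125 Hz is not the same as having no usable acoustic hearing.

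**Conclusion.** The point holds as a matter of precision. The Aim 2 primary model leaves out a prognostic measurement that the plan already obtains at entry and whose subject matter it adjusts for in Aim 1. The loss is about 2% to 18% of the standard error if r lies between 0.3 and 0.6, probably toward the low end, and nothing if r is about 0.2 or below. This assumes roughly equal groups, one summary per subject, and that entry to Aim 2 does not depend on the assigned map.

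It is not a finding of systematic bias. Nor do the documents support a conclusion, which a reader might draw, that a null Aim 2 result could not be interpreted because of hearing loss. The Aim 2 subjects come from Aim 1, where SII is modelled and unaided thresholds are reported, so relevant hearing data are planned for the same people.

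**What to change.** State in the Aim 2 analysis that the mixed models for SRM_EAS, SRM_Contra and localization include the implanted-ear unaided threshold at 125 Hz, measured at activation, as a pre-specified continuous baseline covariate alongside group, interval and their interaction. Name the ear explicitly. Keep all visits in the randomised group, and state that no hearing value measured after randomisation enters the primary model.

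Optionally, and only if unaided thresholds are already measured at later intervals, report an exploratory analysis limited to visits with retained hearing. The documents give no schedule for such measurements. This analysis selects on a value observed after randomisation, so it should be labelled as a non-randomised comparison.

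The cost is a sentence or two of SAP wording and one degree of freedom. The covariate needs no new data, because the threshold is already an eligibility measurement.
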